## (Fasting Condition)

	concomitant use of spironolactone.
	
 
To measure renal clearance (CLR)/Percent Recovered and unchanged drug excreted in urine (fe)/ Amount Recovered for digoxin in the presence and absence of spironolactone (perpetrator) in healthy adult human subjects under fasting condition.
 
To monitor safety of the subjects in drug-drug interaction study.
 

Methodology	This was an open label, balanced, randomized, single-dose, two-treatment, two-sequence, two-period, crossover, drug-drug interaction study in healthy adult human subjects with at least 28 days washout period between each treatment period under fasting condition.
	In both periods (Period-I and II), from Day 1 to Day 5 and Day 7 to Day 9, the subjects who were randomized to treatment B, were administered Spironolactone Oral Suspension 100 mg (Perpetrator; Carospir ® Oral Suspension 20 mL of 25 mg / 5 mL), and the subject who were randomized to treatment A were not dosed. On all these days the standard breakfast was served 0.50 hr (30 min) post dose. On Day 6, after overnight fasting for at least 10.00 hours the subjects were dosed either with the Treatment (A) [LANOXIN ® (digoxin) USP 250 mcg (substrate drug)] or Treatment (B) [LANOXIN ® (digoxin) USP 250 mcg (substrate drug) + Spironolactone Oral Suspension 100 mg (Perpetrator; Carospir ® Oral Suspension 20 mL of 25 mg / 5 mL)] as per the randomization scheme.
	Urine & Blood samples collection were collected after the completion of dosing on Day 6.
	Urine samples
	A total of 11 urine samples were collected from each subject in each study period at intervals of (0.00-1.00), (1.00-2.00), (2.00-4.00), (4.00-6.00), (6.00-8.00), (8.00- 12.00), (12.00-16.00), (16.00-24.00), (24.00-48.00), (48.00-72.00) and (72.00-96.00) hours post dose.
	Immediately out of the total volume of urine collected at each collection time interval, approximately 10 mL (2 x 5 mL aliquots) of urine samples were transferred into two pre-labeled containers for analysis and stored at deep

## (Fasting Condition)

(rasting condition)	Commentia
	freezer maintained at -20°C or lower until dispatched from Clinical Unit to Bioanalytical Department for analysis. After collecting the urine samples from all the subjects at each collection time interval, the total pooled volume was recorded and transferred to analytical site for analysis after the completion of clinical phase.
	Blood samples
	A total of 25 (1 $\times$ 5 mL) blood samples were collected from each subject in each study period at pre-dose (0.00) and at 0.25, 0.50, 0.75, 1.00, 1.33, 1.67, 2.00, 2.33, 2.67, 3.00, 3.50, 4.00, 5.00, 6.00, 8.00, 10.00, 12.00, 16.00, 24.00, 36.00, 48.00, 60.00, 72.00 and 96.00 hours post dose.
	Note: Blood samples up to 3 hours post dose were collected at bed side.
	The pre and post-dose blood samples up to 24.00 hrs were collected via an indwelling cannula and 36.00, 48.00, 60.00, 72.00, and 96.00 post dose samples were collected by a fresh vein-puncture.
	The pre-dose blood sample were collected within 2 hours before dosing and the post-dose in-house samples were collected with a window period of $+ 2$ minutes from the scheduled sampling time.
	The collected blood samples were kept on ice-packs until centrifugation. All the samples except 0.25 hr sample in period I, were centrifuged within 45 minutes from the scheduled blood sample collection. The samples were centrifuged at the set conditions of 4000 rpm for 10 minutes at 4°C to separate plasma. The separated plasma was transferred to pre-labeled polypropylene tubes in two equal aliquots.
	The total amount of blood collected from each subject during the study was about 292 mL
	Subjects were abstained from consuming any alcoholic products from 48.00 hours prior to check-in to till check-out / last sample of the study. They were not allowed to have any xanthine-containing food and/or beverages (like chocolate, tea, coffee, cola drinks), cigarettes and tobacco containing products and grapefruit and/or it's juice from 48.00 hours prior to check-in to till check-out / last sample of the study.

(Tusting Continuon)	
	On Day 6, subjects were fasted for at least 10.00 hours prior to dosing.
	Water was provided ad libitum during the study, except one hour before and one hour after dosing on Day 6.
	On Day 6, subjects who are dosed remained in a supine position or semi recumbent position for 03 hours post-dose and only necessary movement was allowed during this period. Thereafter subject was allowed to ambulate freely during the remaining part of the study. Subject did not sit down (except as directed by the physician secondary to adverse events) during restriction period.
Number of subjects	
 
No. of subjects planned: 28 + 04 (standby subjects)
 
No. of subjects randomized: 28
 
No. of subjects dosed in period I: 28
 
No. of subjects dosed in period II: 28
 
No. of subjects withdrawn: 00
 
No. of subjects dropped out: 00
 
No. of subjects completed the study: 28
 
No. of subjects analyzed in bioanalytical facility: 28
 
No. of subjects analyzed for pharmacokinetic and
 

Diagnosis and main criteria for inclusion	statistical analysis: 28 Healthy consenting human adult subjects between 20 and 35 years of age (both ages inclusive), of Body Mass Index (BMI) within 18.5 to 24.9 Kg/ m  with normal laboratory measurements were included in the study. Subjects weighing less than 60 kg were not enrolled.
Treatment (A)	LANOXIN ® (digoxin) USP 250 mcg (substrate drug), manufactured for Concordia Pharmaceuticals Inc., St. Michael, Barbados BB11005. Initial U.S
LANOXIN ® USP 250 mcg Lot No.	AH3690B
Dose and mode of administration	Single oral dose administered with 120 mL of water under fasting condition.
Treatment (B)	LANOXIN ® (digoxin) USP 250 mcg (substrate drug) manufactured for Concordia Pharmaceuticals Inc., St. Michael, Barbados BB11005. Initial U.S + Spironolactone Oral Suspension 100 mg (Perpetrator; Carospir ® Oral

## (Fasting Condition)

Confidential

	····
	Suspension 20 mL of 25 mg / 5 mL of CMP Development LLC, USA)
(Carospir ® Oral Suspension) Lot No.	1118211
Dose and mode of administration	In case of subjects who were assigned Treatment A, Single oral dose of LANOXIN ® (digoxin) USP 250 mcg was administered with 240 ± 2 mL of water under fasting condition. Subjects swallowed the tablet as a whole. Dosing compliance was assessed by oral cavity check. In case of subjects who were assigned Treatment B, single oral dose of LANOXIN ® (digoxin) USP 250 mcg was administered with 120 mL of water under fasting condition and Carospir ® Oral Suspension 100 mg (20 mL of 25 mg / 5 mL) was administered with 120 mL of water with a graduated syringe. Dosing activity was done under the supervision of cardiologist. CaroSpir oral suspension administration procedure 20 mL of 25 mg / 5 mL of Carospir ® Oral Suspension was loaded in the syringes well in advance prior to dosing on the day of dosing. The suspension in the syringe was rinsed with approximately 10 mL from 120 mL of dosing water and administered to the subjects. This rinsing procedure was done until the syringe was free of the contents of the medication. Then the remaining quantity of water from the assigned 120 ml water was finally administered to the subjects.
Duration of the treatment	A single oral dose of Carospir ® 100 mg Oral (Spironolactone 20 mL of 25 mg / 5 mL) suspension from Day 1 to Day 5 and Day 7 to Day 9 and on Day 6 either LANOXIN ® (digoxin) USP 250 mcg (substrate drug) or LANOXIN ® (digoxin) USP 250 mcg (substrate drug) + Carospir ® 100 mg Oral (Spironolactone 20 mL of 25 mg / 5 mL) suspension (Perpetrator) were administered on 11 Mar 2019 and 08 Apr 2019 in period I and period II, respectively separated by a washout period of 28 days. Total duration of the study from the check in of period I to the last blood draw of period II did not exceed 39 days.
Criteria for evaluation: Safety Evaluation	Subjects were monitored for safety and tolerability during the entire study. The subject's Clinical examination along

## (Fasting Condition)

(rasting Condition)	Connucitia
	with vital signs (seated blood pressure, radial pulse rate and oral/aural temperature) were measured during check-in and check-out of each period.
	Clinical examination was done on prior to dosing on Day 06 in each study period.
	Oral/aural temperature was measured prior to dosing in each study period.
	Vital parameters – seated blood pressure and radial pulse rate were measured at prior to dosing, 1.00, 3.00, 5.00 and 11.00 hours post dose in each period from Day 1 to Day 5, and from Day 6 to Day 9, vitals were measured prior to dosing, at 1.00, 2.00, 3.00, 5.00, 8.00 and 11.00 hours post dose in each period.
	Note
	• On Day 6 the Vital signs (i.e. up to 3.00 hours post dose) was performed at bed side.
	• For subjects who were randomized to treatment A, the vitals were checked at 5.00 hours post dose during day 1 to Day 5.
	ECG was performed at 1.00 and 3.00 hours post dose in each period on Day 6, before period II check-in for subject study eligibility and at check-out of each period of the study. 2D echo was performed at the time of screening.
	In each study period subject's creatinine clearance and serum potassium levels were measured on Day 5 for the dosing eligibility on Day 6.
	For the safety of the subjects, hematology (except blood grouping and Rh typing) and biochemistry (except random blood sugar) investigations were repeated at the end of the study.
Pharmacokinetic Evaluation	The following pharmacokinetic parameters for Digoxin were obtained using non-compartmental method (WinNonlin, version 8.1, Pharsight Corporation, USA):
	$\triangleright$ C max , AUC 0-96 , and t max using plasma data,
	
 
Renal clearance (CLR) /Percent Recovered, Unchanged drug excreted in urine (fe)/Amount Recovered using urine data.
 

Statistical Evaluation	The log-transformed pharmacokinetic parameters $C_{max}$ and $AUC_{0.96}$ were analysed using Type III sum of squares, with

## (Fasting Condition)

Statistical analysis was performed us	
(SAS Institute Inc., USA, Version 9.3).	ing SAS ® package
The presence or absence of DDI treatments (A and B) was concluded ba results of 90% confidence interval f geometric least squares mean for pharmacokinetic parameters C max and A	sed on the statistical or the ratio of the or log-transformed
Absence of drug-drug interaction wou the 90% CI for the ratio of population log-transformed data of $C_{max}$ and AU treatments (A and B), were in the ec 80.00 - 125.00% for Digoxin.	geometric means of JC 0-96 between two

## Summary and Conclusions

Pharmacokinetic & Statistical Results:

#### Table 1: Summary of Plasma Pharmacokinetic parameters for digoxin – Treatment (A)

Treatment	Product/Statistics	C max (ng/mL)	AUC 0-96 (ng.hr/mL)	T max (hr)
	N	28	28	28
	Mean	1530.188	13715.974	0.744
	SD	502.810	2669.003	0.195
Treatment	Min	644.613	8632.172	0.500
(A)	Median	1429.822	13440.345	0.750
	Max	2734.608	21455.761	1.330
	Geometric Mean	1456.085	13473.043	0.721
	CV% Geometric Mean	32.993	19.431	25.996

#### Table 2: Summary of Plasma Pharmacokinetic parameters for digoxin – Treatment (B)

Treatment	Product/Statistics	C max (ng/mL)	AUC 0.96 (ng.hr/mL)	T max (hr)
	N	28	28	28
	Mean	2432.908	16551.500	0.901
	SD	870.562	4108.500	0.569
T ( ( D )	Min	539.707	6373.657	0.500
Treatment (B)	Median	2422.385	17151.091	0.750
	Max	5044.130	23997.624	3.500
	Geometric Mean	2254.118	15996.644	0.810
	CV% Geometric Mean	45.789	28.453	44.310

## (Fasting Condition)

	Geometric Least Square Means and It's Ratio						1
PK Parameters (Unit)	Treatment A	Treatm	ent B	(Treatment A / Treatment B) (%)	ISCV (%)	90% Cl	Power (%)
LOG C max (ng/mL)	1456.085	2254.	.118	64.597	40.07	54.18% to 77.02%	67.47
LOG AUC 0-96 (ng.hr/mL)	13473.043	15996	5.644	84.224	18.56	77.45% to 91.59%	99.56
able 4: Summ	ary of Urine P	harmaco		tic parameters fo	or digoxin	– Treatment (A	4)
Treatment	Product/S	tatistics		enal clearance CLR)/Percent Recovered	unchanged drug excreted in urine (fe)/ Amount Recovered		
	N	N		28		28	
	Mean			54.687		136717.72	
	SD		_	29.158		72895.492	
Treatment A	Min			22.180		55449.800	
Heatment A	Median			46.111		115277.98	
	Max			147.642		369104.30	
	G. Mean			49.042		122606.02	
	G.mean 9	G.mean %CV		48.257		48.257	
able 5: Summa	ary of Urine Pl	harmacc	okinet	ic parameters fo	r digoxin	– Treatment (I	3)
Treatment	Product/S	tatistics		enal clearance CLR)/Percent Recovered		anged drug excr (fe)/ Amount Re	
	N			28		28	
		1					

	IN IN	20	20
	Mean	53.378	133446.07
	SD	21.256	53141.044
Tractment D	Min	21.641	54103.200
Treatment B	Median	51.185	127962.08
	Max	95.602	239003.90
	G. Mean	49.410	123523.87
	G.mean %CV	42.201	42.201

Safety Results	There were no adverse events recorded during the study.			
	Therefore, the safety of the digoxin in the presence and absence of spironolactone would be considered as comparable.			

Conclusion	The exposure ( $C_{max}$ and $AUC_{0.96}$ ) of digoxin was not comparable for the Treatment A and Treatment B. The geometric mean $C_{max}$ was 1456.085 and 2254.118 ng/mL for Treatment A and Treatment B respectively. The geometric mean $AUC_{0.96}$ was 13473.043 and 15996.644 ng.hr/mL for Treatment A and Treatment B respectively By comparing $C_{max}$ and $AUC_{0.96}$ plasma values of Treatment A and Treatment B, we conclude that these values were increased by 35% and 16% respectively for Treatment B. The %Treatment A/Treatment B ratio of digoxin was 64.597% and 84.224% for $C_{max}$ and $AUC_{0.96}$ respectively. The lower and the upper limits at 90% confidence interval were 54.18% - 77.02% and 77.45% - 91.59% for $C_{max}$ and $AUC_{0.96}$ respectively, which were not within the standard equivalence limit of 80.00-125.00%. Based on the above results presence of drug-drug interaction is established between digoxin and spironolactone. The Renal clearance (CLR)/Percent Recovered and unchanged drug excreted in urine (fe)/ Amount Recovered of digoxin was comparable for the Treatment A and Treatment B. The geometric mean Renal clearance
	e i
DATE OF THE REPORT	01 Jul 2019

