## **12.6 SAFETY CONCLUSIONS**

There were no adverse events reported in this study.

Space left blank intentionally.

(Fasting Condition)

Confidential

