### **3 STUDY OBJECTIVES AND PURPOSE**

### 3.1 Objectives

*Primary Objective*: To characterize the pharmacokinetic profiles of Digoxin (substrate drug) in the presence and absence of spironolactone (perpetrator) in healthy adult human subjects under fasting condition.

Secondary objective:

To assess whether there is a drug-drug interaction with concomitant use of spironolactone.

To measure renal clearance  $(CL_R)$ /Percent Recovered and unchanged drug excreted in urine  $(f_e)$ / Amount Recovered for digoxin in the presence and absence of spironolactone (perpetrator) in healthy adult human subjects under fasting condition.

To monitor safety of the subjects in drug-drug interaction study.

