#### Risk evaluation and mitigation strategy:

Since healthy subjects are being enrolled in the study, there is no benefit to them. In general, the adverse reactions of digoxin are dose-dependent and occur at doses higher than those needed to achieve a therapeutic effect. Hence, adverse reactions are less common when digoxin is used within the recommended dose range or therapeutic serum concentration range and when there is careful attention to concurrent medications and conditions.

As Digoxin is a narrow therapeutic index drug, the drug administration will be done under the supervision of a cardiologist along with a continuous close monitoring by medical and para medical personnel. Since most of the digoxin is excreted unchanged in the urine, subjects with significant difference from normal serum creatinine or creatinine clearance values will not be considered for this study. In addition, only the subjects with normal 2D echo and QTc interval will be enrolled into the study.

Considering the single dose nature of this study and 28 days washout period between dosing periods, the effects caused by 250 mcg Tablet of Digoxin are not expected to impact on safety in the healthy volunteer population. Even if adverse events are observed, they are likely to be benign, transient, not require intervention. Nevertheless, close monitoring of blood pressure, pulse rate, and ECG will be conducted during the time maximum pharmacodynamic effects are observed (i.e. during 1 - 3 hours post dose).

Furthermore, subjects will be domiciled until day 04 (i.e. until 96 hours after drug

Protocol for Drug-Drug Interaction Study of Spironolactone and Digoxin (Fasting Condition) Confidential

administration in each period), thus providing an optimal setting for the clinical monitoring and, if necessary, management of any adverse events. However, subjects will only be allowed to leave the clinical center after clinical examination, ECG, and other safety measures are repeated at the end of study visit.

KCl Injection, KCl oral Syrup, Amiodarone Injection 150 mg, Xylocard Injection will be made available in the ICU at the time of study as a precautionary measure. Overall, based on the known AE profile of 250 mcg Tablet of Digoxin, strict screening, inclusion and exclusion criteria, routine safety assessments and planned close monitoring of known AE's, blood pressure, pulse rate, ECG, and 28 days washout period is considered sufficient to mitigate any potential risk to the subjects.

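### The synopsis calls digoxin safety comparable with and without spironolactone because no adverse events were recorded; no safety comparison was planned, and 0/28 under each treatment cannot support that conclusion

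*Protocol*

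**What the plan says.** In the study report, section 2 (Synopsis), under Summary and Conclusions, the Safety Results row has two sentences. The first is descriptive: "There were no adverse events recorded during the study". The second opens with *Therefore* and states that "the safety of the digoxin in the presence and absence of spironolactone would be considered as comparable".

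The rest of the file is more restrained. Section 12.6 (Safety Conclusions) says only "There were no adverse events reported in this study". Section 13 (Discussion and Overall Conclusions) restates the safety objective and draws no comparison of safety between treatments.

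On the planning side, section 3.1 of the appended protocol gives the safety objective as "To monitor safety of the subjects in drug-drug interaction study". Section 10.7 of the protocol and the Statistical Analysis part of the SAP define one equivalence criterion, 80.00-125.00%, and apply it only to digoxin Cmax and AUC0-96. Section 10.1 of the protocol justifies 28 subjects by the aim of estimating the interaction and says nothing about safety event rates.

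**The concern.** The second sentence turns an absence of recorded events into a statement about the difference between two treatments. A claim of comparability needs either a margin chosen beforehand or at least an interval narrow enough to exclude differences that matter. Here there is neither.

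The context gives the sentence weight. The next row of the synopsis concludes that digoxin exposure differed between treatments and that an interaction is established. Section 11.2 of the appended protocol, in its risk evaluation text, begins its monitoring rationale with "As Digoxin is a narrow therapeutic index drug". A statement of comparable safety printed beside a finding of raised exposure may be quoted on its own, and the trial does not supply the evidence for it.

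**Working it through.** **Inputs.** From the synopsis row on number of subjects: "No. of subjects dosed in period I: 28", "No. of subjects dosed in period II: 28" and "No. of subjects withdrawn: 00". Report Table 9 shows 14 subjects in each sequence, all completing. Each subject therefore received both treatments, and no events in the whole study means 0/28 under A and 0/28 under B.

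**Is there a planned safety figure to reproduce?** No. As a check that 28 complete pairs is the right basis, I recomputed the reported Cmax interval from its intra-subject CV of 40.07%:

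- s = sqrt(ln(1 + 0.4007²)) = 0.386
- SE = 0.386 × sqrt(2/28) = 0.103, with 26 degrees of freedom
- 64.597% × exp(±1.706 × 0.103) gives 54.18% to 77.02%, as reported

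**Event rate under each treatment.** With 0/n, the exact upper limit solves (1 - p)^n = α:

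- two-sided 95%: 1 - 0.025^(1/28) = 12.3%
- one-sided 95%: 1 - 0.05^(1/28) = 10.1%

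**Within-subject difference.** This is the quantity that comparability refers to. With no discordant pairs, the score statistic for a true difference δ is δ / sqrt(δ(1 - δ)/n). Setting its square equal to z² gives δ = z²/(n + z²):

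- 95%: 3.84/(28 + 3.84) = 0.121, so about -12.1 to +12.1 percentage points
- 90%: 2.71/(28 + 2.71) = 0.088, so about -8.8 to +8.8 percentage points

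**Chance of seeing nothing under B.** The rates below are my assumptions; the documents give none.

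| Assumed true rate under B | Probability of 0/28 |
|---|---|
| 5% | 0.95^28 = 23.8% |
| 8% | 0.92^28 = 9.7% |
| 10% | 0.90^28 = 5.2% |

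**Ability to detect a difference.** An exact McNemar test at two-sided 5% needs at least six subjects with an event on B only, because 2 × 0.5^5 = 0.0625 but 2 × 0.5^6 = 0.031. Assuming no A-only events, power is 5.5% for a true excess of 10 points and 49.9% for 20 points.

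**Exposure alongside.** Inverting the reported A/B ratios gives B/A = 1/0.64597 = 1.55 for Cmax (90% CI 1/0.7702 to 1/0.5418, that is 1.30 to 1.85) and 1/0.84224 = 1.19 for AUC0-96.

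**The case against.** The sponsor has a fair reply on several counts.

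- *The wording is hedged, and the report uses comparable loosely elsewhere.* The urine results are also called comparable without a test or margin. On that reading the sentence only says that the adverse event record was the same. This fails because *Therefore* presents comparability as a conclusion drawn from the zero count, under a Summary and Conclusions heading.
- *Monitoring was more than spontaneous reporting.* Vital signs and ECGs were taken in each period, creatinine clearance and potassium were measured on Day 5 of each period, and section 11.3 of the protocol counts abnormal laboratory findings as possible adverse events. This stands, and it makes the zero more informative as a description. It does not narrow the interval. The Day 5 tests precede the Day 6 digoxin dose, and the closing hematology and biochemistry panel was done once, at study end, so it gives no separate reading for each treatment.
- *The protocol did not expect a safety effect from this dose in healthy volunteers.* Section 11.2 says so. That explains the zero but also means the setting had little capacity to separate the treatments.

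A reader might go further than the documents allow in three ways. First, one might infer that the whole report concludes safety is comparable. It does not: section 12.6 already has neutral wording, and section 13 is silent. Second, one might infer that the report says the exposure increase is harmless. Nothing in it says that, and the row following the disputed sentence states plainly that an interaction is established. The narrow therapeutic index description also belongs to the appended protocol, not to the report's safety text. Third, one might infer that events under B were missed, because subjects on A had vital signs only at 5 hours on Days 1-5 and adverse event questioning was tied to vital signs. Fewer observations under A cannot hide an excess under B, and the schedules match from Day 6.

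**Conclusion.** The point holds as a reporting overstatement in one synopsis sentence. The data support saying that no adverse events were recorded under either treatment. They do not support comparability: event rates up to 12.3% per treatment, and within-subject differences of about 12 points in either direction, remain compatible with the result, and no margin was set against which to judge them.

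The limits assume independent subjects, a common event probability under each treatment, and complete recording in both periods. The 5%, 8% and 10% rates and the 10- and 20-point excesses are illustrations only, and the conclusion does not depend on them.

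This is not a fault in the design, the SAP or the analysis. It leaves the Cmax and AUC0-96 estimates, their intervals and the interaction conclusion untouched.

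**What to change.** Delete the second sentence of the synopsis Safety Results row and bring the row into line with section 12.6. Suggested text: *No adverse events were recorded under either treatment (0/28 each; exact two-sided 95% upper limit 12.3%). The study was not designed to compare safety, and comparability is not concluded.*

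The limit was not planned, so it should be labelled as descriptive. If the sponsor prefers not to add an unplanned figure, deleting the sentence is the minimum correction. Section 12.6 needs no change. The cost is one sentence, with no new data and no rerun of any planned analysis; the synopsis becomes less favourable in tone but agrees with the body of the report.
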